11.4.3 Secondary analyses

Analyses of secondary outcomes: The secondary outcome, bacterial colonization 14 days after aPDT (measured otherwise the same way as the primary outcome) and bacterial colonization 2 days after for the ORIF midface group will be analyzed in a similar way as the primary outcome (see Section 11.4.2). The proportional odds logistic regression model will additionally adjust for concomitant treatment with nasal rinse therapy, antibiotic therapy, steroid therapy, and nasal decongestant therapy, which are prescribed depending on the surgical intervention, and may also influence bacterial colonization after 14 days. To compare bacterial colonization 5 minutes after aPDT 2 days (only ORIF midface) and 14 days after aPDT (short- and long-term), we analyze these measurements as repeated measurements together in one model. We fit a mixed-effects proportional odds logistic regression model on bacterial colonization, with treatment (intervention vs. control) and time (14 days vs. 5 min and 2 days (only ORIF midface)) as explanatory variables. In an additional model, we will add the interaction between treatment and time, in order to test for a difference in the change over time between the treatment groups.

The colonization with individual types of bacteria (9 types) at baseline, and 5 minutes and 2 days (only ORIF midface) and 14 days after aPDT will be descriptively analyzed and summary statistics (frequency and percentage of each category) will be reported by treatment group.

Subgroup analyses: For the primary outcome, subgroup analyses will be performed for the following subgroups: bacterial colonization at baseline ($>$ median vs \geq median), type of surgery and sex. For each subgroup variable, a proportional odds logistic regression model will be fitted to the primary outcome, with treatment, the subgroup variable, and the interaction between the subgroup variable and treatment as explanatory variables. A statistically significant interaction between one of the subgroup variables and treatment would indicate a different treatment effect in the corresponding subgroups. We will also estimate group-specific treatment effects (with 95 % CI), fitting a separate model for the corresponding subgroups, which will be reported together with the interaction p-value.

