15. INSURANCE	50
16. REFERENCES	51

SYNOPSIS

Objectives	
This study aims to investigate the following objectives in a population of adult patients undergoing surgery under general anesthesia in the department of oral and maxillofacial surgery of University Hospital Zurich:
 
Primary objective:
 
 - to determine the additional efficacy of nasal cavity photodisinfection in reducing local microbial colonization in a preoperative setting compared to 0.2% chlorhexidine gluconate and non-light activated methylene blue. 
Secondary objectives:
 
 - determine the additional efficacy of nasal cavity photodisinfection in reducing local microbial colonization after 14 (+/-1) days follow-up compared to 0.2% chlorhexidine gluconate and non-light activated methylene blue. - additional short-term comparison after 2 days follow-up of patients treated for midface fractures by open reduction and internal fixation (trauma surgery subgroup). - Longitudinal comparison of microbial colonization at baseline, 5 min after aPDT and 14 (+/-1) days after aPDT. - develop an aPDT disinfection protocol for preoperative nasal cavity disinfection at University Hospital Zürich 
Safety objective:
 
 - the safety of nasal cavity photo disinfection by aPDT
Outcomes	
The following outcomes shall be analyzed in patients undergoing surgery under general anesthesia in the department of oral and maxillofacial surgery of University Hospital Zurich:
 
Primary outcome:
 
 - Bacterial colonization 5 minutes after aPDT across the nine analyzed microbe groups, expressed as a score (range 0-27). 
Secondary outcomes:
 
 - Bacterial colonization 14 (+/-1) days after aPDT across the nine analyzed microbe groups and expressed as score (range 0-27). - additional analysis of bacterial colonization 2 days after aPDT for trauma surgery subgroup 
Safety outcome:
 
 - Adverse effects (inquired by standardized survey on first day post intervention and on day 14 (+/- 1d) during regular postoperative follow up.
Design	Randomized controlled prospective single-center double blinded study

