4.2 Primary objective

The primary objective is to determine the additional efficacy of nasal cavity photodisinfection in reducing local microbial nasal colonization in a preoperative setting compared to 0.2% chlorhexidine gluconate and non-light activated methylene blue. Comparison of the 5 minutes after aPDT measure to the control group and to the baseline 3 minutes prior to intervention.

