4.3 Secondary objectives

The secondary objectives are to:

- To determine the efficacy of nasal cavity photodisinfection as an add-on treatment to 0.2% chlorhexidine gluconate in reducing local microbial colonization after 14 (+/-1) days follow-up.
- To analyze short term effects in the critical time for wound healing after 2 days in the subgroup after fracture reduction of the midface
- Longitudinal comparison of microbial colonization at baseline, 5 minutes after aPDT and 14 (+/-1) days after aPDT.
- develop an aPDT disinfection protocol for preoperative nasal cavity disinfection at University Hospital Zürich

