6.2.1 Randomization

Randomization will be performed in REDCap. Clinicians conducting the postoperative surveys will not have access to the eCRF form with the randomization result and therefore be blinded against the treatment group.

Stratified block randomization with variable block size for type of surgery (osteosynthesis removal; open reduction and internal fixation of midface fractures vs other).

Explanation for stratification:

Removal of osteosynthesis material rarely requires any of the under 8.6 mentioned concomitant treatments. In addition, the patients are generally younger and have less comorbidities. Therefore, a stratified randomization to intervention and control group is justified. The second stratification for patients undergoing open reduction and internal fixation of midface fractures is necessary to build the subgroup (target size n=50) with additional swab on day 2 (day of hospital discharge). Also, this patient collective is more consistent in duration of surgery and concomitant treatment.

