9.2.2 Assessment of secondary outcomes

Microbiological testing

The same score ranging from 0-27 is also used to express the colonization 3 minutes before intervention (baseline swab) and 14 (+/-1) days after study or control intervention (follow-up swab). Statistical analysis of baseline, post intervention and follow-up colonization scores allow for understanding the general effects of aPDT on nasal microbiota over a time period of 14 days. Analyzing the difference in microbial colonization scores of experimental and control groups between baseline, 5 minutes post intervention and 14 days after allows quantification of potential influence of concomitant treatment or disinfection effects of unactuated photosensitizer solution (methylene blue, chlorhexidine gluconate).

Only for the subgroup (open reduction and internal fixation of a midface fracture), an additional nasal swab test after 2 days is carried out. This additional testing allows for better understanding of the short-term effects with clinical importance in the initial wound healing. The reason for testing only the subgroup is mainly in the comparable postoperative management in terms of concomitant treatment (single shot antibiotic prophylaxis, CHX mouth rinse, decongestant nasal drops), duration of surgery and hospital stay.

To analyze for shifts within the microbiological colonization without change in total number of CFU, a descriptive subgroup analysis of the nine microbial groups is performed.

Obtaining personal data

Data on concomitant treatments will be taken from clinical information system KISIM.

Survey

The standardized survey for expected aPDT side effects will be conducted during clinical visit on the first postoperative day and regular 14 day (+/- 1d) postoperative follow-up.

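### The longitudinal model in section 11.4.3 omits the baseline swab that its objective names, and its day-2 time contrasts mix change over time with type of surgery

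*Combined protocol and SAP*

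**What the plan says.** The synopsis lists as a secondary objective "Longitudinal comparison of microbial colonization at baseline, 5 min after aPDT and 14 (+/-1) days after aPDT", and section 4.3 repeats it. Section 4.2 adds to the primary objective: "Comparison of the 5 minutes after aPDT measure to the control group and to the baseline 3 minutes prior to intervention". Section 9.2.2 has the same intention: "Statistical analysis of baseline, post intervention and follow-up colonization scores allow for understanding the general effects of aPDT on nasal microbiota".

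Section 11.4.3 contains one repeated-measures analysis, a mixed-effects proportional odds model for the 5-minute, day-2 and day-14 scores, "with treatment (intervention vs. control) and time (14 days vs. 5 min and 2 days (only ORIF midface)) as explanatory variables". A second version adds only the treatment-by-time interaction.

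The day-2 swab is taken only in patients having open reduction and internal fixation (ORIF) of a midface fracture (sections 9.2.2 and 9.3.4). The synopsis expects about 100 such patients, 50 per arm. Section 6.2.1 gives a target of 50 without saying whether that is per arm or in total.

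Type of surgery stratifies the randomization and is named as an adjustment in the primary regression (section 11.4.2). It is not named in the longitudinal model.

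**The concern.** There are two gaps in the same model.

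**Baseline is absent.** The objective names three times and the model drops the first. Followed literally, the plan can say how the score moves from 5 minutes to day 14. It cannot say, with an estimate and interval, how far either time lies from the pre-treatment score.

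**Day 2 comes from one surgical stratum.** The time factor sets day-2 swabs from ORIF patients beside 5-minute and day-14 swabs from all patients. If ORIF patients differ from the rest, part of that difference appears as a change over time. The protocol gives reasons why strata may differ. Section 6.2.1 says of one stratum: "Removal of osteosynthesis material rarely requires any of the under 8.6 mentioned concomitant treatments", and describes those patients as generally younger and with fewer comorbidities. Section 11.4.3 says these treatments are "prescribed depending on the surgical intervention, and may also influence bacterial colonization after 14 days". A reported short-term effect at day 2 could then be partly an artefact of who was swabbed.

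**Working it through.** **1. Where baseline is used**

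| Place | Role of baseline | Gives change in total score? |
|---|---|---|
| 11.4.2 regression, carried over to day 2 and day 14 in 11.4.3 | Adjustment for a between-arm contrast at one time | No |
| 11.4.3 subgroup analysis | Median split | No |
| 11.4.3 descriptive tables | Category frequencies for each of nine bacterial types | No |
| 11.4.3 mixed model | Not included | No |

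This part needs no assumption.

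**2. Size of the day-2 distortion**

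The documents give no figure for this model. From them come N = 208, SD 6 (section 11.2) and the ORIF number n: 100 (synopsis), or 50 if the target in section 6.2.1 is a total. The SD and the 3-point difference in section 11.2 do reproduce the plan's t-test size: 2 × 36 × (1.960 + 1.282)² / 9 = 84.1, so 85 per arm and 170 in all.

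Assumed: a random intercept with within-patient correlation ρ, a constant ORIF-versus-rest difference b, no true time effect, and a linear model on the score scale.

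Solving the generalized least squares equations for treatment plus time:

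- the 5-minute and day-14 levels are both fitted at b × n/N;
- false day-2 versus 5-minute effect = b × (N − n)/N × (1 − ρ)/(1 + ρ).

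For b = 3, n = 100, ρ = 0.5: 3 × 108/208 × 0.5/1.5 = 0.52. The model's standard error is 0.546, so z = 0.519/0.546 = 0.95. The two-sided 5% test rejects with probability Φ(0.95 − 1.96) + Φ(−0.95 − 1.96) = 0.16.

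| b = 3 | ρ = 0.1 | 0.3 | 0.5 | 0.7 |
|---|---|---|---|---|
| n = 100: false effect (SE) | 1.27 (0.70) | 0.84 (0.64) | 0.52 (0.55) | 0.27 (0.43) |
| n = 100: rejection | 44% | 26% | 16% | 10% |
| n = 50: false effect (SE) | 1.86 (0.92) | 1.23 (0.85) | 0.76 (0.73) | 0.40 (0.58) |
| n = 50: rejection | 53% | 31% | 18% | 11% |

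For b = 1 the false effect is 0.42 to 0.09 (n = 100) or 0.62 to 0.13 (n = 50), with rejection of about 6% to 10%.

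Under this constant difference, day 14 versus day 2 has the same bias with opposite sign. The bias in treatment, day 14 versus 5 minutes and treatment-by-time is 0.00.

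**3. Check on the ordinal scale**

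A random-intercept proportional odds model was fitted to one simulated set of 12,000 patients per setting, with a shift of 0.5 SD (Monte Carlo error about 0.05 on the log-odds scale).

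- n = 100: false day-2 odds ratio about 1.5, 1.3, 1.3 and 1.2 at ρ = 0.1, 0.3, 0.5 and 0.7.
- n = 50: about 1.6, 1.6 and 1.3 at ρ = 0.1, 0.3 and 0.5.
- With a surgery term (checked at ρ = 0.3 and 0.5): 0.97 to 1.05.

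**4. Is a surgery main effect enough?**

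Not always.

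- *Strata differ by 3 points at day 14 only.* As written, day 2 versus 5 minutes is off by −0.14 to −0.64 (n = 100, ρ from 0.1 to 0.7). After a surgery main effect is added, the fitted ORIF effect is 1.5 and the 5-minute level is −1.5 × n/N. The day-2 contrast is then −1.5 × (N − n)/N, which is −0.78 (n = 100) or −1.14 (n = 50) at every ρ.
- *Treatment effect differs by 2 points between strata.* Treatment-by-day-2 is off by 2 × (N − n)/N × (1 − ρ)/(1 + ρ). That is 0.85 to 0.18 (n = 100) or 1.24 to 0.27 (n = 50), with or without a surgery main effect.

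A model restricted to ORIF patients is free of both problems.

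**The case against.** The strongest reply is that little of importance rests on the affected contrasts. Day 2 is not in the stated longitudinal objective. The listed day-2 outcome is compared between arms within ORIF patients, in a separate analysis that is sound. The between-arm questions are answered by the baseline-adjusted regressions, and a within-arm change from baseline is not a randomized comparison. All of this stands, and it limits the weight of the point.

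A second reply is that a constant 3-point shift is generous, since it equals the whole treatment effect used for the sample size. The 5-minute swab precedes surgery, so differences in concomitant treatment argue for a post-operative divergence more than a constant one. The younger, healthier patients of section 6.2.1 are the implant-removal stratum, whereas the contrast here is ORIF against implant removal plus all others. Neither the sign nor the size of that difference is documented. This also stands: the figures show what could happen, not what is expected. But a post-operative divergence biases the contrasts too, and a surgery main effect does not repair it. The n = 50 rows rest on the less natural reading of section 6.2.1.

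Third, the opening of section 11 leaves detail to a separate analysis plan. That plan could close both gaps. However, section 11.4.3 already names the time levels and explanatory variables, and a plan that follows it inherits them.

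**Conclusion.** The point holds and should be corrected. That the model does not deliver the stated longitudinal objective is a matter of text and rests on no assumption: change in total score from baseline is never estimated inferentially.

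The day-2 problem is real but conditional. It exists if ORIF patients differ from the rest in level or course. Its size depends on an undocumented stratum difference and correlation, and on a random-intercept structure that the plan implies but does not spell out. It ranges from minor at 1 point to a rejection rate of 10% to 44% at 3 points with 100 ORIF patients.

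The primary test, the sample size of 208, the day-14 between-arm analysis and the ORIF-only day-2 between-arm analysis are unaffected.

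**What to change.** Amend section 11.4.3 and carry the wording into the analysis plan.

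1. Fit the all-patient longitudinal model with baseline, 5 minutes and day 14 as time levels, and with treatment, treatment-by-time and type of surgery as fixed effects. Constraining the arms to be equal at baseline is optional. Alternatively, keep 5 minutes and day 14 as outcomes with baseline score and type of surgery as covariates, and add a stated baseline-to-post analysis.
2. Take day 2 out of the all-patient time factor. Estimate its time contrasts in a longitudinal model restricted to the ORIF midface stratum (baseline, 5 minutes, day 2, day 14).

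The cost is wording and a little more analysis, since every swab is already scheduled. The loss of precision is modest. At correlation 0.5 the ORIF-only standard error for day 2 versus 5 minutes is √(2 × 36 × 0.5/100) = 0.60, against 0.56 in the pooled model with a surgery term. With 50 ORIF patients it is √(2 × 36 × 0.5/50) = 0.85, against 0.76.

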
Inclusion criteria
 
 provision of a signed and dated informed consent form stated willingness to comply with all study procedures and availability for the duration of the study male or female ≥ 18 years of age surgical intervention in general anesthesia with oral intubation at the department of oral and maxillofacial surgery of University Hospital Zurich 	
Exclusion criteria:
 
 inability to tolerate insertion of the light illuminator or the photosensitizer applicator due to anatomic variations (size, shape of oro-nasal region) or disease inability to follow the procedure of the investigation, e.g., due to language problems or psychological disorders of the subject known allergic reactions to components of the nasal decolonization treatment, including methylene blue or chlorhexidine gluconate planned surgery in the nasal cavity necessary nasal intubation for surgical intervention vulnerable persons (subjects incapable of judgment or subjects under tutelage) pregnant or breastfeeding women

Measurements and procedures
 
 microbiological analysis of nasal swabs 3 minutes before and 5 minutes after aPDT standardized survey and nasal swab test during regular postoperative follow up after 14 days (+/- 1 day) additional nasal swab after 2 days before discharge of hospital for midfacial trauma group 	
Measurements:
 
 microbiological analysis of nasal swabs 3 minutes before and 5 minutes after aPDT standardized survey and nasal swab test during regular postoperative follow up after 14 days (+/- 1 day) additional nasal swab after 2 days before discharge of hospital for midfacial trauma group

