11. STATISTICAL METHODS

Detailed methodology for summaries and statistical analyses of the data collected in this study will be documented in a statistical analysis plan. The statistical analysis plan will be finalized before database closure and will be under version control at the Department of Biostatistics, University of Zurich.

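### Does the subgroup definition for baseline colonization in section 11.4.3 leave patients below the median in neither group?

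*Combined protocol and SAP*

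**What the plan says.** Section 11.4.3 of the protocol (Subgroup analyses) names three subgroup variables for the primary outcome: "bacterial colonization at baseline ($>$ median vs \geq median), type of surgery and sex". For each one a proportional odds model is fitted "with treatment, the subgroup variable, and the interaction between the subgroup variable and treatment as explanatory variables". The section continues: "We will also estimate group-specific treatment effects (with 95 % CI), fitting a separate model for the corresponding subgroups".

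The baseline variable is a whole-number score. Section 9.2.2 states: "The same score ranging from 0-27 is also used to express the colonization 3 minutes before intervention (baseline swab". Sections 5.1 and 9.2.1 build that score from nine microbe groups, each rated 0 to 3.

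The cut at the median appears nowhere else. The statistical considerations in the synopsis do not mention these subgroup analyses, and the rest of section 11 adds nothing on the cut. Section 11 leaves detailed methods to a separate, version-controlled document: "The statistical analysis plan will be finalized before database closure".

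**The concern.** A score strictly above the median is also at or above it, so the first group lies wholly inside the second, and nobody below the median belongs to either. The interaction model needs two exclusive levels that together cover all patients. As it reads, the definition does not supply them.

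The score is also discrete, so a noticeable number of patients can fall exactly on the median. If the cut were chosen only after outcomes by arm were visible, the placement of those patients could be steered, and with it the interaction p-value and the two subgroup odds ratios.

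A further question is whether splitting at the median is sensible at all, or whether the interaction should use the numeric baseline score.

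**Working it through.** **1. Membership as the text reads.** Let m be the median baseline score.

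| Baseline score | In `> m` | In `≥ m` | Groups |
|---|---|---|---|
| below m | no | no | none |
| equal to m | no | yes | one |
| above m | yes | yes | both |

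The literal reading is therefore unusable for the interaction term. The separate models could technically be run on overlapping sets, but the interaction factor cannot be built.

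**2. The possible corrections.** Changing one sign gives one of two splits:

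- change the first sign: `< m` versus `≥ m`, ties in the upper group;
- change the second sign: `> m` versus `≤ m`, ties in the lower group.

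Each puts every patient in exactly one group, and each carries its own tie rule. Changing only the first sign also keeps ties where the text already places them, in the group at or above the median.

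**3. How many patients depend on which correction is used.** The documents give no baseline distribution, so this step rests on assumption. For a normal score with standard deviation s, rounded to whole numbers and centred on a whole number, the share at the median is P = 2Φ(0.5/s) − 1. The value s = 6 borrows the planning standard deviation of the primary outcome in section 11.2; 4 and 3 are assumed.

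| s | P | P × 208 |
|---|---|---|
| 6 | 0.066 | 14 |
| 4 | 0.099 | 21 |
| 3 | 0.132 | 28 |

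Simulation of rounded scores with 198 evaluable patients gave about 13 ties (s = 6) to 26 ties (s = 3). The `<` versus `≥` split then gives about 92 versus 106 (s = 6) or 86 versus 112 (s = 3). The other split gives nearly the mirror image. Both remain usable median splits.

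**4. Slip or misreading?** In the text as read from the PDF, the first sign sits between math delimiters and the second is a bare typesetting command. Elsewhere the sign is clean, as in the inclusion criterion "male or female ≥ 18 years of age". The damage falls exactly where the apparent error lies, so this text cannot show whether the page itself is wrong.

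**5. Would a numeric interaction be better?** An illustrative simulation used 4,000 replicates per cell, 198 patients, outcome standard deviation 6, a mean effect of −3, and a linear model rather than the planned proportional odds model. Power of the interaction test, for assumed baseline–outcome correlations 0 / 0.3 / 0.5 / 0.7:

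| Assumed shape of the effect | Numeric score | Median split |
|---|---|---|
| changes 2 points per baseline SD | 0.633 / 0.684 / 0.746 / 0.885 | 0.439 / 0.497 / 0.541 / 0.657 |
| steps by ±1.6 points at the median | 0.311 / 0.332 / 0.409 / 0.541 | 0.458 / 0.477 / 0.533 / 0.605 |

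The ranking reverses with the assumed shape, and the documents say nothing about which shape to expect.

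**The case for a change.** The strongest case for acting is that the definition is wrong as it reads, no other section repairs it, and one line would put it right. The tie rule is not trivial on a 0–27 integer scale: the two corrections send perhaps 7% to 13% of patients to opposite groups. Finalizing the analysis plan before database closure does not by itself guarantee that nobody has seen outcomes by arm when the choice is made.

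The set logic stands, and so does the point that the text does not reveal which correction was meant. The harm does not follow so readily. It requires the cut to be chosen late and with knowledge of results, and nothing in the documents suggests this. The median comes from the baseline score alone and needs no outcome data. Section 11.4.6 requires deviations to be listed and justified, so an unusual choice would be visible. A separate complaint about ties fails because correcting either sign settles them. The argument for a numeric interaction is a matter of preference: it gains power under one assumed shape of effect and loses it under another.

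**Conclusion.** No change to the plan follows. The signs in section 11.4.3 do not define two groups as they read, but this is either a slip of a single sign or a misreading of the PDF. It announces itself as soon as the factor is coded. Any analyst will take it as an ordinary median split, and the analysis plan still to be finalized is where such detail is normally written down.

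The consequence is confined to one of three secondary subgroup variables. The choice between the two possible splits affects about 14 to 28 of 208 patients, on assumed baseline standard deviations of 6 to 3. The primary Wilcoxon-Mann-Whitney test, the adjusted model, the sample size of 208 and all stated figures are untouched. Replacing the split with a numeric interaction is a trade-off without a clear gain.

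The conclusion assumes that the split is settled from baseline data before results by arm are known, which the arrangements in sections 11 and 11.4.6 make the natural course.

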11.1 Hypothesis

The two-sided null hypothesis to be tested is that nasal cavity photodisinfection by aPDT (intervention) as an add-on treatment to 0.2 % chlorhexidine gluconate has no effect on local microbial colonization in a perioperative setting compared to 0.2 % chlorhexidine gluconate and non-light activated methylene blue (control). The corresponding alternative hypothesis is that the two treatments differ. The research hypothesis is, that the intervention will reduce local microbial colonization compared to control (superiority of the intervention).

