11.2 Determination of sample size

The sample size was calculated to show the superiority of the intervention compared to the control regarding the primary outcome with a power of 90 % at a significance level of 5 %. We calculated the sample size for a Wilcoxon-Mann-Whitney test, but did this via the sample size for a two-sample t-test and by increasing the sample size using the Asymptotic Relative Efficiency (ARE) of the Wilcoxon-Mann-Whitney test (compared to the t-test), which is never less than 0.864 (17,18). The power was estimated for a range of sample sizes $n_{i=1,\dots,61} = 50,\dots,350$ with the R package sse (19). Moreover, to assess how the calculation is affected by the mean difference, θ , we varied θ from 1.5 to 4.5. For each combination of n_i and θ , we calculated the power for a two-sample t-test.

Figure 1 shows that for showing a mean difference in the primary outcome of 3 with a standard deviation of 6, a total of 170 evaluable patients would be required for a two-sample t-test. For a Wilcoxon-Mann-Whitney test we increased the sample size, dividing 170 by 0.864, which resulted in 198 patients (rounded up to an even number). Assuming a drop-out rate of 5 %, 208 patients need to be enrolled.

[figure not shown]

Figure 1: Dependence of the sample size on the mean difference between treatments, θ , assuming a standard deviation of 6. An example is shown for $\theta=3$ and a power of 90 %. The curves are smoothed and shown for illustration only.

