11.4.2 Primary analysis

The primary outcome, bacterial colonization 5 minutes after aPDT across the nine analyzed microbe groups, expressed as a score (range 0–27), will be compared between the randomized groups (intervention vs. control) by an exact Wilcoxon-Mann-Whitney test, as implemented in the function of `wilcox_test` from the R package `coin` (20), for an improved handling of ties (compared to other implementations of the test). We will also estimate the Mann-Whitney parameter, $\varphi = \Pr[X < Y] + 0.5\Pr[X = Y]$ (with X and Y being the ordered primary outcome in the intervention and control group), a natural effect parameter associated with this test with a corresponding 95 % confidence interval. In addition, we will apply a proportional odds logistic regression model, in order to adjust for the baseline measurement of bacterial colonization and the type of surgery used for stratifying the randomization. The primary outcome will be analyzed as ordinal outcome with type of surgery and randomized treatment (intervention vs. control) as explanatory variables. This model will estimate proportional odds ratios with 95 % confidence intervals.

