13. PUBLICATION AND DISSEMINATION POLICY

After the statistical analysis of this study, the sponsor-investigator will make every effort to publish the data in a medical journal. In the case of results of public interest, a summary will be provided in lay language. The sponsor-investigator will have final authority over all activities. In this study, an analysis of gender effects will be conducted, and the respective results will be published in the final study report.

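### The subgroup models in 11.4.3 leave out the baseline score and surgery stratum, which loses precision if baseline is prognostic and may put subgroup odds ratios on a different scale from the overall one

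*Combined protocol and SAP*

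**What the plan says.** For the primary outcome, 11.4.3 plans subgroup analyses by baseline colonization (split at the median), type of surgery and sex. Each uses a proportional odds model "with treatment, the subgroup variable, and the interaction between the subgroup variable and treatment as explanatory variables". The effects to be reported come from further fits: "We will also estimate group-specific treatment effects (with 95 % CI), fitting a separate model for the corresponding subgroups". No covariates are named for these.

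The overall proportional odds model in 11.4.2 is introduced "in order to adjust for the baseline measurement of bacterial colonization and the type of surgery used for stratifying the randomization". The synopsis (Statistical considerations) gives the same two adjustment variables, and section 5.1 says the primary results are adjusted to baseline. However, when 11.4.2 lists that model's explanatory variables, it names only type of surgery and randomized treatment.

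Section 13 commits to the sex analysis being reported: "an analysis of gender effects will be conducted, and the respective results will be published in the final study report".

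**The concern.** The subgroup models analyse the same outcome as the overall model but do not carry its stated covariates:

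- **Sex model:** no baseline score and no surgery stratum.
- **Surgery-type model:** no baseline score.
- **Baseline model:** no surgery stratum.
- **Separate within-subgroup models:** no stated adjustment.

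Two things are at stake. The first is precision. Every patient has a baseline swab, and ignoring it costs most where patients are fewest. The second is comparability. The odds ratio is non-collapsible, so leaving out a prognostic covariate moves it towards 1 even when the arms are perfectly balanced. If the overall odds ratio is baseline-adjusted and the subgroup ones are not, they do not estimate the same quantity, and a homogeneous effect can look weaker in every subgroup.

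**Working it through.** **Inputs from the plan.** Section 11.2 assumes a "mean difference in the primary outcome of 3 with a standard deviation of 6", 90% power and a 5% level, and arrives at 198 evaluable patients after the Wilcoxon inflation. The test is two-sided (11.1) and allocation is 1:1 (7.3).

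**Inputs assumed, because the documents do not give them.** The correlation rho between the baseline and 5-minute scores (0 to 0.7), the size of the interaction, and equal subgroups.

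**The plan's own figure.** Per arm, 2 × (1.960 + 1.282)² × 6² / 3² = 84.1, rounded up to 85, so 170 in total (noncentral t power 0.900). Then 170 / 0.864 = 196.8, rounded up to an even 198, and 198 / 0.95 = 208.4 against the stated 208. The sample size reproduces within rounding. It covers the overall comparison only; no power is stated for any interaction.

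**Interaction power, normal approximation.** With two equal subgroups, SE = 4 × 6 / √198 = 1.71 points. Adding baseline multiplies this by √(1 − rho²). Power is Φ(interaction / SE − 1.96). For 3 points without baseline, 3 / 1.706 − 1.96 = −0.20, which gives 42%.

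| rho | SE with baseline | Power, 3 points | Power, 1.5 points |
|---|---|---|---|
| 0 (same as unadjusted) | 1.71 | 42% | 14% |
| 0.3 | 1.63 | 45% | 15% |
| 0.5 | 1.48 | 53% | 17% |
| 0.7 | 1.22 | 69% | 23% |

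**Check with the planned type of model.** Proportional odds models were fitted to simulated 0–27 scores (198 patients, 1,000 trials per setting, 3-point interaction, equal subgroups). Power without and with baseline was 45% and 45% at rho 0, 44% and 47% at 0.3, 41% and 54% at 0.5, and 43% and 72% at 0.7. The Monte Carlo standard error of each figure is about 1.6 points (√(0.25 / 1,000)). The pattern matches the approximation.

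**Odds ratio scale.** In the same runs (odds ratio below 1 meaning lower scores with the intervention), the average treatment odds ratio without and with baseline was:

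| rho | Without baseline | With baseline | Shift in log odds ratio |
|---|---|---|---|
| 0 | 0.40 | 0.40 | 0.00 |
| 0.3 | 0.398 | 0.376 | 0.06 |
| 0.5 | 0.407 | 0.344 | 0.17 |
| 0.7 | 0.413 | 0.270 | 0.42 |

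For comparison, the standard error of a log odds ratio in a subgroup of 99 is about 0.36 from fitted models; the rough formula √(12 / 99) gives 0.35. Around 0.40, that is a 95% interval of about 0.20 to 0.81. The shift is a sixth of a standard error at rho 0.3, just under half at 0.5, and more than one at 0.7.

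**Not quantified.** The gain from adding type of surgery, and power for the surgery-type interaction. Section 6.2.1 appears to define three surgery categories, so the two-subgroup formula does not carry over.

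**The case against.** **The lists are read unevenly.** If the term list in 11.4.3 is taken as complete, the list in 11.4.2 should be too, and that one also omits baseline. The overall odds ratio would then be unadjusted for baseline, the surgery-type model would hold the same variables as the overall model plus the interaction, and the sex model would lack only the stratum. This stands. The scale mismatch depends on how 11.4.2 is reconciled; the loss of precision does not.

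**The gain rests on an unknown correlation.** Both arms receive the chlorhexidine and methylene blue formulation between the two swabs (8.1.1, 8.1.2), so rho could be low. At rho 0 nothing is gained and at 0.3 about 3 points of power. This also stands. So does the point that a 3-point interaction equals the whole planned effect: at 1.5 points, power is 14% to 23% whatever is done.

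**Readers will see confidence intervals and the interaction p-value.** That largely answers the worry about misreading at low and moderate rho, though not at 0.7.

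**Detail is deferred to a later SAP.** Section 11 does say so. But 11.4.3 already specifies these models, and its remark about analysing outcomes similarly to the primary one covers only the 14-day and 2-day outcomes. The deferral makes the SAP a suitable place for the correction; it does not supply one.

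**Equal covariate lists do not guarantee one scale.** Separately fitted models can still differ in residual variation and baseline range. True; matching the covariates removes the avoidable part of the difference.

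**Conclusion.** The omission is real, and no other section fills it. Its main consequence is lost precision, conditional on baseline being prognostic, which the plan presumes when it proposes to adjust for it. For a 3-point interaction in equal subgroups of 198 patients, adding baseline raises approximate power from 42% to 45%, 53% or 69% at assumed correlations of 0.3, 0.5 or 0.7, and by nothing at 0. Provided the overall model is baseline-adjusted as its purpose clause says, unadjusted subgroup odds ratios will also tend to lie closer to 1. That shift is small at low correlation and notable only at high correlation.

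A reader might go further in three ways that the documents do not support:

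- **That the subgroup tests are invalid.** They are not; under randomization the unadjusted interaction tests stand.
- **That the subgroup table will definitely show a misleading attenuation.** This needs both a baseline-adjusted overall model and a high correlation, and the documents settle neither.
- **That adjustment would make the interactions adequately powered.** The trial was sized for the overall comparison, and small interactions stay poorly powered either way.

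The primary Wilcoxon-Mann-Whitney test and the sample size are unaffected. This is a worthwhile, nearly free improvement to secondary analyses.

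**What to change.** In 11.4.3, or in the SAP before database closure:

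- Add the continuous baseline score and type of surgery as covariates to the sex and surgery-type interaction models (in the latter, type of surgery is already present as the subgroup variable).
- Add the same covariates to the separate within-subgroup models, omitting type of surgery within a surgery type.
- In the baseline-subgroup interaction model, keep the planned subgroup term and its interaction with treatment, and add type of surgery.

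In 11.4.2, reconcile the listed terms with the stated purpose, so that it is clear whether the overall odds ratio is baseline-adjusted.

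This needs no new data, visits or patients. The cost is a few extra parameters in the smaller within-subgroup models. Fixing the covariates in advance also closes off a choice made after seeing the data.
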